## **17. ANALYSIS**

### **17.1 Safety Analysis**

The first safety analysis will be conducted when 20 subjects have completed study treatment. Additional analysis will be done every 20 patients. A brief report will be generated describing any adverse events experienced and number of subjects that were unable to complete IP treatment.

### **17.2 Efficacy Analysis**

Efficacy analysis will be conducted at the completion of the study.

### **17.3 Interim Analysis**

An interim analysis for futility will be performed when 18 patients per group have completed their radiation therapy treatment. A conditional power analysis will be performed based on the data accumulated to date. Briefly, the observed results will be used to generate predicted results for future patients (assuming a normal distribution) with the observed mean and standard deviation observed in each group. One thousand bootstrap samples with a sample size of 36 patients per group (target sample size) will be generated to estimate conditional power. The study will continue if the conditional power is  $> 80\%$ . Note that this analysis is for futility only, so will not affect the overall alpha level.

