## 1. INTRODUCTION

### 1.1 Phase:

This is a phase II, single center, randomized, double-blind, placebo-controlled study assessing the effects of dexamethasone versus placebo on radiation fatigue, quality of life (QoL), and treatment interruption in patients receiving definitive treatment for head and neck and non-small cell lung cancers. Subjects will be stratified by treatment (radiation alone vs. radiation plus systemic therapy) and randomized within strata to one of two treatment arms with equal probability.

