## 16. STATISITICAL CONSIDERATIONS

Statistical analysis will be performed in collaboration with [name], the Director of the University of Arizona Cancer Center Biometry Shared Service. The primary outcome is the change in the fatigue score between radiation days 15 (day prior to IP initiation) and 26 (day after IP completion) in the dexamethasone versus placebo patients as measured by the Functional Assessment of Chronic Illness-Fatigue (FACIT-F) 13-item fatigue subscale. Secondary endpoints include the QoL score as measured by the FACIT-F 40-item total score, and the total days and cause of treatment interruption. Randomization will be stratified by tumor location and treatment type (radiation alone versus radiation plus systemic therapy). Analysis of the continuous endpoints (change in FACIT-F fatigue subscale and change in FACIT-F total score) will be performed using a two-sample independent t test comparing the dexamethasone versus placebo patients. Analysis of the total days of treatment interruption will be performed using a Wilcoxon Rank Sum Test, since the number of days may not be normally distributed. Alternatively, the proportion of patients with any treatment interruptions will be compared using a Fisher's Exact Test.

The sample size of 40 patients per group was chosen based on the previous study of Yennurajalingam et al. in advanced cancer patients with at least three cancer-related fatigue symptoms. They observed a mean improvement in the FACIT-F fatigue score of 9.0 (standard deviation = 10.30) in the dexamethasone treated group versus a mean improvement of 3.1 (standard deviation = 9.59) in the placebo group. We chose a one-sided statistical test (at the alpha = 0.05 level) as dexamethasone will only be recommended in our patient population if it improves cancer-related fatigue. Based on these considerations, 36 patients per group will provide 80% statistical power. We rounded the necessary sample size up to 40 patients to allow for the possibility of up to a 10% drop-out of patients from their radiation therapy between days 16 and 26.

Exploratory analyses will profile the change in the FACIT-F fatigue subscale and FACIT-F total score across the entire radiation therapy course (measured at baseline screening, on RT days 5, 10, 15, 20, 25, 26, and 30, and 60 day follow-

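### The 80% conditional-power rule in Section 17.3 stops 42–49% of trials in which dexamethasone works exactly as assumed, and cuts the stated 80% power to about 49–55%

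*Combined protocol and SAP*

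**What the plan says.** Section 16 sizes the trial from an earlier study in advanced cancer: "They observed a mean improvement in the FACIT-F fatigue score of 9.0 (standard deviation = 10.30) in the dexamethasone treated group". For placebo, the corresponding figures it gives are 3.1 points with an SD of 9.59. The test is one-sided at 0.05, and the section concludes that "36 patients per group will provide 80% statistical power". Enrolment is raised to 40 per group for drop-out. No allowance is made for an interim look.

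Section 17.3 places a futility analysis at 18 patients per group who have finished radiation therapy. Outcomes for future patients are drawn from normal distributions with the means and SDs seen so far in each group. The procedure is: "One thousand bootstrap samples with a sample size of 36 patients per group (target sample size) will be generated to estimate conditional power". The decision rule is: "The study will continue if the conditional power is" greater than 80%. The section adds that a futility-only look leaves the overall alpha level alone. It does not mention power, does not call the rule advisory, and gives no other ground for continuing.

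**The concern.** A futility rule should stop a trial that has little chance of success. This one stops any trial whose projected chance of success is 80% or less. The projection uses the interim estimate itself, which is noisy at 18 per group. The trial was designed with about 80% power at the assumed effect, so an interim result that matches the design assumption only just passes.

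An observed interim difference of 5.0 points, for example, projects to about 75% conditional power when the 18 observed patients per group are kept. The rule would still stop that trial as futile. At stake is a high risk of abandoning an effective treatment, together with a power statement that does not describe the design as written.

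**Working it through.** **Inputs.** Means 9.0 and 3.1, so a difference of 5.9; SDs 10.30 and 9.59; one-sided alpha 0.05; 36 evaluable per group (Section 16). Equal allocation (Section 1.1). Interim at 18 per group and continuation above 80% (Section 17.3). The information fraction is t = 18/36 = 0.5.

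**Reproducing the plan's figure.** Pooled SD = √((10.30² + 9.59²)/2) = 9.951. Then n = 2 × 9.951² × (1.645 + 0.842)² / 5.9² ≈ 35.2, so 36 per group, and 36/0.9 = 40. Power at 36 per group is 80.8% by the normal approximation and 80.1% by the noncentral t. The stated sample size is therefore right for a trial without an interim look.

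**Expected Z statistics at the design effect.**
- Final: 5.9 / (9.951 × √(2/36)) = 2.515.
- Interim: 5.9 / (9.951 × √(2/18)) = 5.9 / 3.317 = 1.779.
- Correlation between the two: √0.5.

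**Interim cut.** Section 17.3 can be read in two ways.
- Reading A keeps the 18 observed per group and simulates 18 more. Conditional power is Φ((Z₁/√t − 1.645)/√(1−t)). It exceeds 0.80 when Z₁ > √0.5 × (1.645 + 0.842 × √0.5) = 1.584, an observed difference of 1.584 × 3.317 = 5.25 points.
- Reading B simulates all 36 per group afresh. The probability is Φ(Z₁/√t − 1.645). It exceeds 0.80 when Z₁ > √0.5 × (1.645 + 0.842) = 1.758, an observed difference of 5.83 points.

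The bar is therefore 89% (A) or 99% (B) of the assumed effect.

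**Consequences.** P(stop) at the design effect is Φ(1.584 − 1.779) for A and Φ(1.758 − 1.779) for B. Power is P(Z₁ > cut and Z₂ > 1.645) from the bivariate normal. Simulated figures come from 40,000 trials with t tests and 1,000 draws at each interim.

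| | No look | Reading A | Reading B |
|---|---|---|---|
| Stop, design effect | – | 42.3% (sim. 41.9%) | 49.2% (sim. 49.1%) |
| Power | 80.8% (sim. 79.9%) | 54.9% (sim. 54.9%) | 48.9% (sim. 48.7%) |
| Stop, no effect | – | 94.3% | 96.1% |
| One-sided alpha | 5% | 2.1% | 1.7% |

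At the design effect, about 61% (A) or 65% (B) of the stopped trials would have been significant at 36 per group.

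**Sensitivity.** If all 40 per group are evaluable at the end and the interim rule still targets 36, power is 55.4% (A) or 49.2% (B), against 84.3% without the look. A third reading, 18 observed plus 36 further patients per group, would stop 33% and leave 62% power, but it conflicts with 36 being described as the target. With a true effect of 7 points, larger than assumed, the rule still stops 30% (A) or 36% (B).

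**The case against.** The strongest objection is that a binding stop is inferred. Section 17.3 says when the study continues; it does not say that a lower value obliges stopping, or who decides. If the result is only advisory, the loss is smaller and cannot be fixed in advance. That assumption has to be stated. Stopping is nevertheless the plain meaning: this is the only continuation condition in a futility section, Section 11.6 has the DSMB reports cover predetermined futility stopping rules, and nothing makes the rule non-binding.

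It is also fair that the rule cannot create a false positive. The statement that alpha is not raised is correct, and the harm is a loss of power, not of validity. How strict a futility rule should be is the sponsor's choice, and a single-centre phase II trial might accept a demanding one. That choice would be defensible if its cost were disclosed, but Section 16 still promises 80%.

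Finally, the two readings differ in degree. Asking for nearly the full design effect describes Reading B; under Reading A the bar is somewhat lower. Section 17.3 does not settle which applies, and neither keeps power near 80%.

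**Conclusion.** The concern holds. With a true difference of 5.9 points, SDs of 10.30 and 9.59, a one-sided 0.05 test, and stopping whenever conditional power is 80% or less, the design has about 55% power under Reading A and 49% under Reading B. An effective treatment at the planning effect is abandoned at the interim 42% or 49% of the time. Sections 16 and 17.3 are inconsistent on power, and one of them has to change. This should be settled before any interim data are seen, because a later change to the rule would lack credibility.

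**What to change.** In Section 17.3, say whether the 18 observed patients per group are kept in the projection, state what happens when the condition fails and who decides, and replace the threshold with a futility bound whose power cost is given.

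One example is to stop only if conditional power is below 30%, keeping the observed patients and assuming the 5.9-point effect for the remainder. Here conditional power is Φ(Z₁ + 1.779 − 1.645/√0.5) = Φ(Z₁ − 0.547), so the cut is Z₁ = 0.023, an observed difference of about 0.1 point.

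The alternatives, all keeping the 18 observed per group, compare as follows (normal approximation):

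| Stop if conditional power is | Stop, design effect | Stop, no effect | Power |
|---|---|---|---|
| Below 30%, design effect assumed | 4.0% | 50.9% | 80.0% |
| Below 10%, observed trend | 10.4% | 69.9% | 77.4% |
| Below 20%, observed trend | 15.0% | 77.1% | 75.0% |
| 80% or less, observed trend (now) | 42.3% | 94.3% | 54.9% |

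The choice among these is the sponsor's. Milder rules stop fewer trials early when the drug has no effect, and that is the real price of the change. If the present rule is kept, Section 16 should state power of about 55% (Reading A) or 49% (Reading B) in place of 80%. Either route takes about one sentence in each section and no additional patients.

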## **18. REGULATORY OBLIGATIONS**

### **18.1 Informed consent**

Before a subject's participation in the clinical study, the investigator or identified designee is responsible for obtaining written informed consent from the subject or legally authorized representative after adequate explanation of the aims, methods, anticipated benefits, and potential hazards of the study and before any protocol specified procedures, investigational product, intervention or device are administered or initiated.

### **18.2 Institutional Review Board**

A copy of the protocol, proposed ICF, and all other applicable subject information will be submitted to the IRB for written approval. A copy of the written approval of the protocol and ICF must be on file at the institution before recruitment of subjects into the study.

The investigator is responsible for obtaining IRB approval/renewal at least annually throughout the duration of the study. Copies of the investigator's reports and the IRB continuance of approval must be on file at the institution.

The investigator must submit study information to the IRB as required by all applicable guidelines and requirements. The investigator will obtain IRB approval for subsequent protocol amendments; except changes to eliminate an immediate hazard to study subjects, and changes to the informed consent document from the IRB prior to implementation.

The investigator will notify the IRB of deviations from the protocol or serious adverse events occurring at the site and other serious adverse event reports occurring at or received from participating centers as applicable for multi-center trials following the IRB policies and procedures.

## **19. ADMINISTRATIVE PROCEDURES**

### **19.1 Investigator responsibilities**

The PI will conduct this study in accordance with the current International Conference on Harmonization (ICH) guidance, the Good Clinical Practice (GCP) guidance, the Declaration of Helsinki, FDA regulations, local IRB and legal requirements.

### **19.2 Data and Safety Monitoring Board protocol review**

Initial DSMB protocol review will be conducted prior to SRC and IRB submissions.

### **19.3 Multicenter Trials** Not applicable

#### **19.3.1 UACC DSMB and QA/QC Monitoring**

The UACC QA/QC Program will be responsible for routine monitoring of local study data for the coordinating center.

#### **19.3.2 Alternate DSMB Oversight** Not Applicable

## **20. SUBJECT CONFIDENTIALITY**

The principal investigator will ensure that the subject's confidentiality is maintained in compliance with Federal regulations, the International Conference on Harmonization (ICH), and Good Clinical Practice (GCP) Guidelines.

Oversight entities and/or regulatory authorities will be permitted direct access to review the subject's original medical records, electronic medical records or certified copies for verification of study-related procedures and data. Direct access includes examining, analyzing, verifying, and reproducing any records and reports that are important to the evaluation of the study.

## **21. STUDY DOCUMENTATION AND ARCHIVE**

The investigator will maintain a list of appropriately qualified persons to whom he has delegated study duties. All persons authorized to make entries and/or corrections on case report forms (CRF) will be included on the Delegation of Responsibilities Form.

Source documents, data, and records from which the subject's CRF data are obtained include, but are not limited to, hospital records, clinical/office/research charts, laboratory and pharmacy records, diaries, microfiches, radiographs, and correspondence. Source data will include information necessary for the reconstruction and evaluation of the trial.

The principal investigator or sponsor-investigator is responsible for maintaining a comprehensive and centralized filing system of all study-related (essential) documentation as required per ICH Guidelines. This can be accomplished by the PI, through the site's standard operating procedures and/or the institutions infrastructure.

The investigator will follow ICH Good Clinical Practice Guidelines and the Code of Federal Regulations for records and record retention.

## **22. DATA**

Applicable data as specified as required in the protocol will be reported/submitted in the CRF. Data reported in the case report forms that are derived from source documents must be consistent with the source documents or the discrepancies must be explained. CRFs will be completed via the paper and OnCore. In addition, data will be entered into RedCap which is currently being used by many UMC departments for their study data bases.

Additional procedures and assessments may be performed as the institution's standard of care; however these data should remain in the medical records and should not be provided as part of the clinical study data unless it pertains to a serious adverse event.

The investigator is required to prepare and maintain adequate and accurate case histories that record all observations and other data pertinent to the investigation on each individual administered the investigational product.

## **23. PROTOCOL DEVIATIONS**

The investigator will conduct the study in conformance with this protocol, generally accepted standards of Good Clinical Practice and all applicable federal, state and local laws, rules, and regulations.

Approvals or waivers for protocol deviations will be obtained from the investigator prior to occurring, except changes to eliminate an immediate hazard to study subjects. If immediate verbal approval is obtained, it will be documented by the

research staff obtaining the approval and followed by a written protocol deviation form per the site standard operating procedures. The investigator will sign the Protocol Deviation (Waiver) Approval Form or other similar document. The original will be filed in the regulatory binder and a copy will be placed in the subject's research file.

## 24. KARNOFSKY PERFORMANCE STATUS SCALE DEFINITIONS

Able to carry on normal activity and to work; no special care needed.	100	Normal no complaints; no evidence of disease.
	90	Able to carry on normal activity; minor signs or symptoms of disease.
	80	Normal activity with effort; some signs or symptoms of disease.
Unable to work; able to live at home and care for most personal needs; varying amount of assistance needed.	70	Cares for self; unable to carry on normal activity or to do active work.
	60	Requires occasional assistance, but is able to care for most of his personal needs.
	50	Requires considerable assistance and frequent medical care.
Unable to care for self; requires equivalent of institutional or hospital care; disease may be progressing rapidly.	40	Disabled; requires special care and assistance.
	30	Severely disabled; hospital admission is indicated although death not imminent.
	20	Very sick; hospital admission necessary; active supportive treatment necessary.
	10	Moribund; fatal processes progressing rapidly.
	0	Dead

## 25. COMMON TOXICITY CRITERIA

CTCAE version 4.0

## 26. STUDY SCHEDULE

	Baseline screening	RTD1	Weekly	RTD15	RTD16	RTD20	RTD25	RTD26	RTD30 **	Last Day of RT	30 & 60 day F/U
			During RT (+/- 2 RT Days)								
Informed Consent/Enrollment	X										
Medical history (1)	X										
Physical exam and KPS (2)	X								X **	X	X
Assess recent/concurrent meds (3)	X										
Hematology (4)	X										
Tumor info and treatment (5)	X										
Registration	X										
Randomization	X										
FACIT-F total QoL (6)	X		X	X 		X	X		X	X	X
Dispense Medication				X							
Investigational Product (7)					X			X 12			
Pill Diary				X				X 12			
Observation Form (11)				X				X		X	X
RPG fingerstick (8)				X		X	X			X 	X 
Adverse event evaluation		X	X	X		X	X		X	X	X
RT treatment interruptions										X	

1 = Medical history will include demographics (this can be done within the last 60 days prior to registration as part of standard of care)

2 = All physical exams to include vitals (BP, pulse, temperature, weight) (this can be done within the last 60 days prior to registration as part of standard of care)

3 = Review current medications including corticosteroid, psychostimulant, and systemic cancer treatments in past 30 days

4 = Hematology to include Hgb and ANC within the last 90 days as part of standard of care, or after consenting, but prior to first treatment

5 = Confirmation of cytologic or histologic evidence of HN or non-small cell lung cancer

6 = QoL survey, 27 questions (completed ± 2 RT days from scheduled time point)

7 = Start IP and take for 14 consecutive days, unless IP stopped due to elevated RPG

8 = RPG fingerstick (completed ± 2 days from scheduled time point). IP will be stopped if RPG ≥ 250

9 = Survey to be completed the day before IP initiation

10 = RPG per physician discretion

27. GLOSSARY: Not applicable

28. DEFINITIONS: Not applicable

### **30. APPENDIX**

- 30.1 Treatment Plan Calendar
- 30.2 FACIT-F 13 item fatigue subscale
- 30.3 FACIT-F 40 item total score
- 30.4 Patient Observation Form
- 30.5 Patient Pill Diary
- 30.6 Pharmacy Information Form
- 30.7 Pharmacy Order Form
